3 OBJECTIVES AND OUTCOME MEASURES/ENDPOINTS

It is hypothesised that HIV infection could be a risk factor for more severe MPX outcomes and that advanced immunodeficiency as defined by current CD4 T-cell count or CD4 T-cell nadir is a risk factor for more severe MPX outcomes in PLWHIV.

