3.1 Primary objective

1. To describe and compare outcomes of MPX in People Living with HIV (PLWHIV) and a HIV-negative population of people using pre-exposure HIV prophylaxis (PrEP users)
2. To identify risk factors for specific MPX outcomes (including CD4 cell count nadir and current CD4 count in PLWHIV)

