6.2 Data collection

Only real-world retrospective data will be used for this study. Patients who have had mpox and fulfil the entry criteria will be enrolled after 90 days from date of diagnosis to allow for follow up data to be collected. Pseudonymised retrospective data will be transcribed into the eCRF system from source data at each clinical site or from existing cohort databases, where appropriate. No personal identifiable data will be transmitted to NEAT ID. The data elements will be transcribed from source data according to the data collection list below. Mechanisms to ensure data quality and integrity will be deployed as per applicable standard operating procedures and in line with Good Documentation Practice (GDocP) and Good Pharmacoepidemiology Practice (GPP). Patients will be identified and documented by participating sites.

For all patients with MPX the following information will be collected where routinely available:

- Age (year of birth)
- Sex and gender identity
- Ethnicity (where available)
- HIV status
- HIV pre-exposure prophylaxis (PrEP) use
- Comorbidities and Medical history (diabetes mellitus, other immunosuppression (e.g. solid organ transplant), known chronic kidney or liver disease, mental health conditions)
- Recent sexual history (3 months) – number of recent partners
- Recent and/or concomitant sexually transmitted infections
- Orthopoxvirus vaccination history (if available)
- Symptom onset date (fever onset, lesion onset, rectal pain)

- Date of positive PCR test result (documented)
- MPX severity -Reported clinical signs and symptoms of mpox (e.g. rash, mouth lesions, rectal pain, breathlessness)
- Time to resolution of lesions, if known
- Mortality as a consequence of MPX including cause
- Hospitalisation for MPX and length of hospitalisation
- Drug treatment for MPX (Tecovirimat, other)
- Drug for complications associated with MPX (laxatives, antibiotics, analgesia)
- recent travel to/living in endemic country or country with outbreak
- contact with suspected, probable, or confirmed case (if known)
- contact with infected animal (if known)

For PLWHIV the following additional information will be collected:

- Date of HIV diagnosis
- Current Antiretroviral Therapy/Treatment (ART)
- If not on ART, reason for not being on ART
- Last CD4 cell count (including CD4% and CD4/CD8 ratio) and
- Last HIV-RNA before MPX diagnosis

Skin lesion at peak severity score:

- Not presenting with skin lesions (0 skin lesions)

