The second primary outcome analysis will be performed between PLWHIV with MPX versus PrEP users with MPX. The endpoint is to assess differences in clinical manifestations of MPX between the groups. Unadjusted and adjusted odds ratios (ORs) will be calculated using the logistic regression models to compare the rates of clinical manifestations between PLWHIH and PrEP users. The adjusted variables will be the following (potential confounders): Age (<30 vs 30-40 vs >40 years); Sex at birth (female vs male); Comorbidities; multiple sexual partners (yes vs no); number of sexual partners in the last 3 months prior to MPX diagnosis; and smallpox vaccination history (yes vs no).

The third primary outcome analysis will be performed within the PLWHIV group. The endpoint is to evaluate the characteristics of HIV infection associated with severe mpox. Univariable and multivariable logistic regression models will be used to assess factors associated with severe mpox in PLWHIV. The following variables will be evaluated: time since HIV diagnosis (years); current ART; CDC disease stage; CD4 cell nadir; last CD4 cell count/HIV-RNA before MPX diagnosis (including CD4% and CD4/CD8 ratio). Variables achieving $P < 0.20$ in the univariable analysis will be retained for the multivariable analysis.

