7.7 Procedure(s) to account for missing or spurious data

Multiple imputation using Chained Equations approach (MICE) will be used to fill in missing data. Ten imputations (M=10) will be chosen to obtain valid inference and reduce sampling variability resulting from the imputation process. Variables with a missing rate above 20% will be excluded and the outcomes will be included in the imputation model. All 10 datasets will be analyzed and combined using Rubin rules. A complete case analysis will also be performed as a sensitivity analysis to assess the robustness of the results.

8 Consent

Due to the nature of this data collection study, consent will not be sought.

In order to maintain confidentiality, the participant will be identified only by subject number. Participant data will be collected from electronic health records by appropriately trained and authorised member(s) of the study team who must be identified and authorised in writing by the Principal Investigator (PI). A delegation of responsibility log will be updated accordingly.

As data collection is entirely retrospective, participants will not need to attend any additional visits. Participants will not have undergone any procedures above their routine standard of care.

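### The third primary model may admit up to five overlapping immune markers on P<0.20 alone, so the adjusted CD4 odds ratio may be attenuated, imprecise or hard to interpret for primary objective 2

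*Combined protocol and SAP*

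**What the plan says.** Primary objective 2 (section 3.1) is: "To identify risk factors for specific MPX outcomes (including CD4 cell count nadir and current CD4 count in PLWHIV". The hypothesis in section 3 is that "advanced immunodeficiency as defined by current CD4 T-cell count or CD4 T-cell nadir is a risk factor". It joins current CD4 and nadir with an 'or', as two ways of defining one condition.

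The analysis that serves this objective is the third primary analysis in section 7.4: "Univariable and multivariable logistic regression models will be used to assess factors associated with severe mpox in PLWHIV". Besides time since HIV diagnosis and current ART, its candidates are "CDC disease stage; CD4 cell nadir; last CD4 cell count/HIV-RNA before MPX diagnosis (including CD4% and CD4/CD8 ratio". Five of these describe immune status: last CD4 count, CD4%, CD4/CD8 ratio, CD4 nadir and CDC stage. Selection is by univariable P<0.20: variables that meet it "in the univariable analysis will be retained for the multivariable analysis". No confounders are listed for this analysis, although the first two primary analyses each have a list.

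Two other sections bear on which markers are available. For people with HIV, section 6.2 lists "Last CD4 cell count (including CD4% and CD4/CD8 ratio) and" HIV-RNA, but neither CD4 nadir nor CDC stage. Section 7.7 adds: "Variables with a missing rate above 20% will be excluded and the outcomes will be included in the imputation model".

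**The concern.** The selection rule looks at one variable at a time. If immune status matters for severity, each marker of it is likely to show a univariable association, and several will enter together. The coefficient for last CD4 then describes the effect of CD4 with the other immune measures held fixed, which is not the question in objective 2. For example, CD4% expresses the CD4 count as a share of lymphocytes, so with CD4% held fixed a difference in CD4 count reflects a difference in total lymphocytes.

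The hypothesis treats current CD4 and nadir as alternatives, whereas the model can make them compete with each other and with three further markers. A real association with immunodeficiency could be split across several terms, none of them clearly different from 1, and be reported as no independent effect of CD4. The univariable odds ratio does not have this problem, but it is not adjusted for age, comorbidities or vaccination.

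**Working it through.** The documents give no effect size, event count or power for this analysis, so there is no planned figure to reproduce. The check asks what the written rule does under stated assumptions.

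**Inputs from the documents.** Total size is about 2000, with the split between groups not given (section 4). Two event rates stand in for severe mpox: 53/907 = 5.8% hospitalised among people with HIV on the dashboard (section 6.1), and 13% hospitalised in the early report of all patients (section 1).

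**Assumptions.** There are 800 or 1000 people with HIV, which gives about 46 to 130 events (800 × 0.058 = 46; 1000 × 0.13 = 130). Five markers share a common pairwise correlation r of 0.4, 0.6 or 0.8, with CDC stage then made binary at 20%. The true odds ratio is 1.6 per SD of worse status. Two mechanisms are considered: a shared immune status drives severity and each marker measures it with noise, or last CD4 itself drives severity.

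**Closed-form approximation, shared status, all k markers entered, β = ln 1.6 = 0.470.**
- Single-marker OR = exp(β√r): 1.35, 1.44, 1.52 for r = 0.4, 0.6, 0.8.
- Joint OR = exp(β√r / (1 + (k−1)r)). With k = 5: exp(0.470 × 0.632/2.6) = 1.12; exp(0.470 × 0.775/3.4) = 1.11; exp(0.470 × 0.894/4.2) = 1.11.
- Standard-error ratio = √[(1 + (k−2)r) / ((1−r)(1 + (k−1)r))]. With k = 5: √(2.2/1.56) = 1.19; √(2.8/1.36) = 1.43; √(3.4/0.84) = 2.01.

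If last CD4 is the driver, the joint and single odds ratios are both about 1.6 and only the standard error changes.

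**Simulation of the actual rule** (univariable screen at P<0.20, then the joint model; 400 runs per scenario). Results for last CD4 with 1000 people with HIV are shown as 5.8% / 13% events:

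| Mechanism | r | All five enter | OR, one marker | OR, joint | SE ratio | Significant, one marker | Significant, joint |
|---|---|---|---|---|---|---|---|
| Shared status | 0.4 | 39% / 76% | 1.33 / 1.33 | 1.17 / 1.14 | 1.16 / 1.17 | 56% / 86% | 11% / 16% |
| Shared status | 0.6 | 61% / 91% | 1.43 / 1.44 | 1.12 / 1.13 | 1.39 / 1.41 | 76% / 96% | 8% / 16% |
| Shared status | 0.8 | 80% / 97% | 1.52 / 1.52 | 1.13 / 1.13 | 1.94 / 1.94 | 85% / 98% | 6% / 10% |
| CD4 is driver | 0.4 | 16% / 36% | 1.61 / 1.61 | 1.54 / 1.57 | 1.11 / 1.14 | 92% / 100% | 78% / 99% |
| CD4 is driver | 0.6 | 49% / 73% | 1.60 / 1.61 | 1.52 / 1.59 | 1.36 / 1.39 | 91% / 100% | 59% / 93% |
| CD4 is driver | 0.8 | 69% / 95% | 1.57 / 1.60 | 1.53 / 1.59 | 1.91 / 1.93 | 88% / 100% | 31% / 69% |

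Across all scenarios, including 800 people with HIV, 2.8 to 5.0 of the five markers enter on average, and all five enter in 12% to 97% of runs. Under a shared status, the one-marker OR of 1.33–1.53 (significant in 52–98% of runs) becomes 1.12–1.21 (4–16%). With CD4 as the driver, 1.57–1.61 (85–100%) becomes 1.51–1.60 (30–99%). The one-marker fits contain no confounders, so they only approximate the models proposed below.

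**The case against.** A reader might infer that the plan puts all five markers in together and so removes the CD4 effect. The text does not support that. Entry depends on P<0.20, and at low correlation and low event rate all five seldom enter. The rule on more than 20% missing may drop some markers. The plan also reports univariable CD4 estimates, which the other markers cannot distort. Attenuation is not certain either: if last CD4 is the driver, its odds ratio is nearly preserved. Nor does the check show that signs would reverse.

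The bracket around CD4% and CD4/CD8 ratio could mean alternative forms of one measurement. Equally, if the section 6.2 list is complete, nadir and CDC stage will not be there to enter. Either reading alone leaves three markers. With k = 3 the closed form gives a joint OR of exp(0.470 × 0.632/1.8) = 1.18 at r = 0.4 and exp(0.470 × 0.894/2.6) = 1.18 at r = 0.8, so the problem shrinks but remains. If both readings hold, only last CD4 is left and the overlap disappears, but then the nadir part of objective 2 has no data.

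Finally, objective 2 names nadir and current CD4, so asking what each adds given the other is legitimate, and the study describes itself as mainly descriptive. That justifies one declared model with those two terms. It does not justify letting a P-value screen decide which of five markers adjust for one another.

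**Conclusion.** The concern holds as a defect in a stated rule: overlapping immune markers can enter one model with only P<0.20 as a filter, and no CD4 measure is nominated or kept in. The adjusted CD4 odds ratio may then be attenuated, imprecise or hard to interpret. No planned model gives a CD4 effect that is adjusted for confounders and free of this problem.

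The size is conditional. Under a shared immune status, which fits the section 3 hypothesis most naturally, the odds ratio per SD falls to 1.12–1.21. If last CD4 is the driver, the harm is mainly a wider interval. The standard error ratio is 1.1 to 1.95 across both. The correlations, the number of people with HIV and the true odds ratio are assumed. Hospitalisation is only a proxy for severe mpox, since the UK definition in section 6.2 also counts other features. The stronger conclusion, that the CD4 effect will be adjusted away, is not established.

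**What to change.** In section 7.4, replace the screened joint model with two pre-specified models of severe mpox in people with HIV: one with last CD4 count as a continuous term, one with CD4 nadir. Do not screen the CD4 term on its P-value. Give each model a fixed, named confounder set. The list already used for the first two primary analyses would serve: age, sex at birth, comorbidities, sexual partners and smallpox vaccination. Leave AIDS, which Appendix 1 lists as a comorbidity, out of the comorbidity term, or immune status returns by that route. Do not add current ART or last HIV-RNA to the nadir model by default, because both may follow the nadir.

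Use CD4%, CD4/CD8 ratio and CDC stage only as one-at-a-time substitutes in sensitivity analyses. If the mutual question is wanted, pre-declare one further model with last CD4 and nadir together.

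Reconcile sections 7.4 and 6.2: confirm that nadir is captured before relying on its model, and either collect CDC stage or remove it. State in advance what happens to the nadir model if nadir exceeds the 20% missing limit in section 7.7.

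The cost is SAP wording and possibly one added data item if nadir is not already captured (a second if CDC stage is kept). A reader might take this as a wording change only, but that is true only once nadir is confirmed as collected. The downside is that no mutually adjusted effect is reported for each marker.

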7.5 Secondary outcome analysis

All secondary outcome analysis will be performed on PLWHIV with MPX compared to PrEP users with MPX.

The prevalence of MPX per site during the study period will be estimated by the number of MPX patients attending the site divided by the total number of patients the sites saw during the study period. The 95%

Confidence Interval of the prevalence will be calculated with the exact Clopper-Pearson method. Fisher exact test will be used to compare the prevalence of MPX in HIV-infected individuals to that of PrEP users.

The length of stay in hospital will be estimated using competing risk models with death as a competing event. Gray's test will be used to compare the duration of hospitalisation between PLWHIV and PrEP users. Unadjusted and adjusted sub-distribution hazard ratios (sHR) will be calculated using competing risk models with death as a competing event. The duration of hospitalization will be defined by the time (days) from hospitalization to hospital discharge or last observation. Adjustment variables will include: Age (<30 vs 30-40 vs >40 years); Sex at birth (female vs male); Comorbidities; multiple sexual partners (yes vs no); number of sexual partners in the last 3 months prior to mpox diagnosis; and Orthopoxvirus vaccination history (yes vs no).

Subgroup analyses for clinical manifestation in MPX will be conducted to assess the difference between PLWHIV and PrEP users across comorbidities. The following comorbidities will be assessed: diabetes mellitus, immunosuppression (e.g. solid organ transplant), chronic kidney or liver disease, mental health illness. Adjusted odds ratio will be calculated to compare PLWHIV and PrEP users within subgroup using logistic regression models. Adjustment variables will include: Age (<30 vs 30-40 vs >40 years); Sex at birth (female vs male); multiple sexual partners (yes vs no); number of sexual partners in the last 3 months prior to mpox diagnosis; and smallpox vaccination history (yes vs no).

Heterogeneity in the impact of HIV infection on clinical manifestations based on comorbidities will be assessed by including terms for interactions between patient status (PLWH and PrEP users) and the comorbidity variable in multivariable logistic regression models. All variables described above for adjustments will be included in the multivariable models.

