Full study Title:	Morbidity, Mortality And Risk Factors of Mpox in HIV negative high-risk Sexual health clinic attenders and People Living With HIV - MASH Study	
Short title/Acronym	MASH	
Clinical Phase	Observational Retrospective Cohort Study	
Study Design	Case-descriptive study	
Study Population	PLWHIV (people living with HIV) who are currently sexually active and HIV negative high-risk Sexual Health Clinic attenders (PrEP users) with Mpox	
End of study data collection	Date of clinical resolution e.g. lesion resolution, hospital discharge or death (up to 3 months)	
Planned Sample Size	Approximately 2000	
Eligibility Criteria	at least 18 years of age with either documented HIV-1 infection or PrEP clinic attenders, and confirmed MPX infection by documented result on PCR testing on skin and/or mucosal and/or any anatomical site.	
Indications	HIV & MPX; PrEP patients & MPX	
Methodology	Only real-world, routinely collected, retrospective data will be used for this study collected from patients who during the study period have had confirmed Mpox. Pseudonymised data will be transcribed into the eCRF (electronic Case Report Form) system from source data at each clinical site or from existing databases, where appropriate. No personal identifiable data will be transmitted to NEAT ID.	
Number of sites	Up to 12 sites in up to 7 countries	
Objectives	
Primary
 
 1. To describe and compare outcomes of MPX in PLWHIV and an HIV-negative population of people using pre-exposure HIV prophylaxis (PrEP users) 2. To identify risk factors for specific MPX outcomes (including CD4 cell count nadir and current CD4 count in PLWHIV) 	
Secondary
 
 1. To estimate the approximate prevalence of MPX in PLWHIV and PrEP users in this retrospective cohort 2. To describe clinical manifestation of MPX and response to MPX treatment in PLWHIV and PrEP users 3. To describe the co-morbidities in PLWHIV and PrEP users

Outcome Measures	Primary	Secondary

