	
 1. Severity of lesions, clinical complications, percentage of hospitalisations, death. 2. Differences in the clinical manifestation of MPX in PLWHIV and PrEP users 3. Differences in the clinical manifestation of MPX in PLWHIV by CD4 and VL 	
 • Number of MPX patients attending as a percentage of total number of patients the sites have seen over a set period of time (first Mpox patient to last Mpox patient at site) • time to lesion resolution (if known) • Length of stay in hospital • Differences in the clinical manifestation of MPX in PLWHIV and PrEP users by comorbidities.

LIST OF ABBREVIATIONS

Acronym	Description
ACCI	Age-adjusted Charlson Comorbidity Index
ART	Antiretroviral Therapy/Treatment
ARV	Antiretroviral
CCI	Charlson Comorbidity Index
CI	Chief Investigator
CRF	Case Report Form
CRO	Contract Research Organisation
CTA	Clinical Trial Authorisation
EC	European Commission
ECMO	Extracorporeal Membrane Oxygenation
eCRF	Electronic Case Report Form
EMEA	European Medicines Agency
EU	European Union
EUCTD	European Clinical Trials Directive
GDPR	General Data Protection Regulation
GDocP	Good Documentation Practice
GPP	Good Pharmacoepidemiology Practice
HIV	Human Immunodeficiency Virus
ICH	International Conference on Harmonisation of technical requirements for registration of pharmaceuticals for human use.
ISF	Investigator Site File
ISPE	International Society for Pharmacoepidemiology
MS	Member State
MPX	MPox (previously known as Monkeypox)
MSM	Men who have sexual activity with men
PI	Principal Investigator
PLWHIV	People living with HIV
PrEP	Pre-exposure prophylaxis
PrEPHRA	HIV negative, high risk sexual health clinic attenders
R&D	Research & Development
REC	Research Ethics Committee
SOP	Standard Operating Procedure
TMF	Trial Master File
VFD(s)	Ventilator-Free Day(s)
WHO	World Health Organisation

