3.4 Secondary endpoints/outcomes

- Number of MPX patients attending as a percentage of total number of patients the sites have seen over a set period of time (from first Mpoxy patient to last Mpoxy patient**)
- Length of stay in hospital*** for inpatients treated for MPX.
- Time to lesion resolution (if known)
- Differences in the clinical manifestation of MPX in PLWHIV and PrEP users by co-morbidities.

*Hospitalisations for clinical reasons only (i.e. not for precautionary measures or quarantine).

** This is regardless of if these first and last patients were included in the collected data

***in case of multiple hospitalisations, this will be the sum of the length of all stays.

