5.1 Inclusion Criteria

- Diagnosis of MPX was more than 90 days prior to data collection
- Confirmed MPX infection by documented PCR testing on skin and/or mucosal and/or any anatomical site between 1st May 2022 to 1st December 2023
- At least 18 years of age
- Cases (PLWHIV + MPX)
 - Documented HIV-1 infection
- Cases (PrEP users + MPX)
 - Attended a clinic to receive PrEP or self-procured PrEP at time of Mpox diagnosis.

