6 STUDY PROCEDURES

6.1 Participant Identification

Most People living with HIV (PLWHIV) and HIV negative PrEP users will be identified from sites in the NEAT ID network. PLWHIV are routinely followed-up at specialised outpatient clinics with regular follow up visits as standard of care and many of these centres take care of patients on PrEP. Patients are taking PrEP to prevent contraction of HIV as they perceive themselves to be at risk due to frequent sexual activity with different partners.

In July 2022, NEAT ID opened a dashboard to 150 sites from 20 countries to provide basic information about the number of PLWHIV with MPX and disease outcomes at their centres (<https://www.NEAT-ID.org/>). Data were provided from patients' cases from April 2022 until November 2022 from 31 global sites, 26 sites from 16 European countries and 5 site in Latin America. The dashboard provided a first estimate about the total numbers of PLWHIV with MPX and where these patients are in continued care. As of the end of November 2022, 907 PLWHIV with MPX were reported in care, with 53 hospitalisations and 1 death from an estimated number of 85,279 PLWHIV in routine care at these sites ([name] *et al*, EACS 2023). These case numbers strongly suggested feasibility to recruit sufficient numbers of PLWHIV with MPX and that patients have been identified at their centres already.

A feasibility study of patients receiving PrEP across the NEAT ID network have identified 45 sites that provide PrEP services for a total of 27,416 PrEP users with 1,361 new PrEP initiators each month.

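### The mpox prevalence endpoint has two denominators: patients seen between a site's first and last case (synopsis, 3.4) and patients seen in an undated study period (7.5)

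*Combined protocol and SAP*

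**What the plan says.** The endpoint is the number of mpox patients as a percentage of all patients seen. Its time window is described in three places.

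- Synopsis, secondary outcome measures: "over a set period of time (first Mpox patient to last Mpox patient at site".
- Section 3.4: "over a set period of time (from first Mpoxy patient to last Mpoxy patient". A footnote adds: "This is regardless of if these first and last patients were included in the collected data".
- Section 7.5: the number of mpox patients attending is "divided by the total number of patients the sites saw during the study period".

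Section 7.5 asks for this prevalence per site with a Clopper-Pearson interval, and adds a group comparison: "Fisher exact test will be used to compare the prevalence of MPX in HIV-infected individuals to that of PrEP users".

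The study period has no dates anywhere. The synopsis methodology refers to "patients who during the study period have had confirmed Mpox", which points to the diagnosis window in section 5.1, "between 1st May 2022 to 1st December 2023". Section 7.4 uses the same term for the point at which unhealed lesions are censored.

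**The concern.** One endpoint, serving the first-listed secondary objective, has two denominators, and the analysis section does not use the one in the endpoint definition. The footnote in 3.4 shows that the first-to-last rule was written on purpose, so it is not simply loose wording for the study period.

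The 3.4 window also has a weakness of its own: it opens and closes on the event being counted. Every case at the site falls inside it by construction, while patients seen only before the first case or after the last are dropped from the denominator. The percentage therefore tends to rise, and the window length varies by site with the timing of that site's cases. Two sites with the same cases and the same clinic volume can report different prevalences only because one had an early or late isolated case.

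At stake are the per-site prevalences, any pooled figure and the Fisher comparison. If the windows are left unreconciled, sites could return attendance counts over different periods, or the window could be chosen once the data are in hand.

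**Working it through.** The documents state no prevalence, precision or power for this endpoint, so there is no planned figure to reproduce. The check asks how far the choice of window could move the result.

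**Inputs**
- Diagnosis window (5.1), taken as the most natural reading of the study period: 1 May 2022 to 1 December 2023 = 579 days; 579 / 30.4375 = 19.02 months.
- PrEP feasibility figures (6.1), 45 network sites: "27,416 PrEP users with 1,361 new PrEP initiators each month".
- Dashboard figures (6.1): 907 mpox cases among 85,279 PLWHIV in care; 907 / 85,279 = 1.06%.
- Assumptions: every current PrEP user is seen, nobody stops PrEP, and the case count is the same under both windows. Span lengths are illustrative. Seven months matches the reporting period of one centre's data set in section 2 (15 May to 15 December 2022), which is not a first-to-last-case interval.

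**PrEP prevalence**

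Denominator for a window of m months: D(m) = 27,416 + 1,361 × m. With cases fixed, prevalence under the shorter window is multiplied by D(19.02) / D(m), where D(19.02) = 27,416 + 25,890 = 53,306.

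| Case span (months) | D(m) | Factor |
|---|---|---|
| 18 | 51,914 | 1.03 |
| 15 | 47,831 | 1.11 |
| 12 | 43,748 | 1.22 |
| 7 | 36,943 | 1.44 |
| 3 | 31,499 | 1.69 |

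**Comparison of groups**

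The group ratio moves only if the two denominators grow differently. Take PLWHIV as a closed group of 85,279, with the share seen in m months equal to min(1, m / visit interval). Set PrEP cases so that prevalence is equal over 19.02 months: 0.010636 × 53,306 = 567. Then shorten the window to 7 months, which gives PrEP prevalence 567 / 36,943 = 1.535%.

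- PLWHIV visits every 3 or 6 months (assumed): all are seen and prevalence stays at 1.064%. The PLWHIV/PrEP ratio is 1.064 / 1.535 = 0.69, Fisher p about 1e-11.
- PLWHIV visits every 12 months (assumed): the denominator is 85,279 × 7/12 = 49,746 and prevalence is 1.823%, up by a factor of 12/7 = 1.71. The ratio is 1.823 / 1.535 = 1.19, p about 0.001.
- PLWHIV visits at random times with a mean interval of 6 months (share seen 1 − exp(−m/6); PrEP cases reset to 592 for equality over 19.02 months): ratio 0.96, p = 0.49.

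With an 18-month window and regular visits, the ratio is 0.97 (p = 0.63).

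So the window alone can produce an apparent difference in either direction, or almost none, depending on case span and visit pattern.

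**The case against.** The best defence is that the study period in 7.5 may be shorthand for the set period in 3.4. Because the term is undated, it cannot be shown that the authors meant 19 months, or that the two descriptions are irreconcilable. That stands as a limit on the claim. It does not remove the defect: no text links the two, and 7.5 cannot be programmed until the term has dates.

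A reader might infer that the two windows do give materially different results. The documents do not support this. They give no site's first or last case date, and if cases span most of the 19 months the difference is negligible. The inflow figures come from 45 feasibility sites and the PLWHIV figures from 31 dashboard sites, not from the up to 12 study sites.

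A reader might also infer a known direction of bias between groups, on the view that PrEP numbers grow while PLWHIV numbers are stable. Nothing in the documents establishes that stability, and the denominator is patients seen, not patients in care. The direction reverses with the assumed visit interval.

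A site with a single case would have a one-day window. This follows from the rule, but it is an extreme: section 7.1 expects an average of about 170 patients per site.

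Nor is the first-to-last window certain to be the shorter one. The footnote lets patients outside the collected data set its limits, and the dashboard in 6.1 includes cases from April 2022, before eligibility opens.

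Finally, an outbreak-period percentage can be a legitimate deliberate choice. That is a reason to keep it as a labelled analysis over common dates. It does not justify different dates at each site.

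**Conclusion.** The inconsistency holds on the text alone: the endpoint definition and its analysis use different windows, and one of them is undated. The first-to-last window is also a poor choice in itself, because it depends on the outcome and varies between sites.

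The numerical effect is conditional. It ranges from about 3% on PrEP prevalence for an 18-month span to 22% for 12 months and 44% for 7 months, given the network inflow, no one leaving, and the diagnosis window as the study period. A shift in the group comparison is possible but is established in neither size nor direction.

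Section 3.2 calls this an approximate prevalence, and no primary analysis uses it. The point should be corrected before attendance counts are requested or analysed, but it does not threaten the main conclusions of the study.

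**What to change.** State one dated calendar window for all sites and both groups in the synopsis, 3.4 and 7.5. The eligibility window, 1 May 2022 to 1 December 2023, is the natural choice. Define the study period by those dates wherever it refers to prevalence. Count the cases and the unique patients seen over the same dates, separately for PLWHIV and PrEP users. If an outbreak-period figure is wanted, report it as a sensitivity analysis over one calendar sub-period common to all sites and fixed before the counts are examined.

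The cost is a wording change in three places, and each site runs its attendance query over fixed dates instead of its own case dates. Reported prevalences may be somewhat lower than under the first-to-last rule.
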